4.5.1. Liver Chemistry Stopping Criteria

Liver chemistry stopping and increased monitoring criteria have been designed to assure subject safety and evaluate liver event etiology (in alignment with the FDA premarketing clinical liver safety guidance).
<http://www.fda.gov/downloads/Drugs/GuidanceComplianceRegulatoryInformation/Guidances/UCM174090.pdf>

Study treatment will be discontinued **for a subject** if liver chemistry stopping criteria are met:

Figure 2 Phase I Liver Chemistry Stopping Criteria – Liver Stopping Event Algorithm

Liver Safety Required Actions and Follow up Assessments Section can be found in [Appendix 2](#) (Section 11.2).

4.5.1.1. Study Treatment Restart or Rechallenge

Study treatment restart or rechallenge after liver chemistry stopping criteria are met by any subject participating in this study is not allowed.

4.5.2. QTc Stopping Criteria

A subject that meets either bulleted criterion below will be withdrawn from the study.

- QTcF > 500 msec,
- Change from baseline: QTc > 60 msec

For trial eligibility the same QT correction formula (QTcF) will be used. The same QT correction formula (QTcF) will be used for all QTc data being collected for data analysis. Discontinuation decisions would ideally use the same QT correction formula will be used. The exception would be safety ECGs or other non-protocol specified ECGs outside the control of the clinical unit.

Withdrawal of subjects is to be based on an average QTc value of triplicate ECGs. If an ECG demonstrates a prolonged QT interval, then obtain 2 more ECGs over a brief (e.g.,

5-10 minute) recording period and then use the averaged QTc values of the 3 ECGs to determine whether the subject should be discontinued from the study.

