3. STUDY DESIGN

3.1. Overall Design

Study 204856 will be a randomized, double-blind (sponsor unblind), placebo controlled trial in three Parts.

1. Part 1, will be a single-dose (SD), dose-rising study in healthy subjects. Subjects will receive GSK3008356 (or matching placebo), as a single dose in each of five sequential cohorts while receiving a standard 30% fat meal. The initial dosing for the first cohort will be staggered so that 2 subjects will be dosed as sentinel subjects. Provided there are no safety concerns, the remainder of the subjects scheduled for the cohort may be dosed.

2. Part 2, will be a 14-day, repeat-dose (RD), dose-rising study in healthy subjects. Subjects will receive GSK3008356 (or matching placebo), as 14 daily doses in each of three sequential cohorts. Day 1 and day 14 dosing for the first cohort will occur while receiving a standard 30% fat meal. The final two cohorts will receive the same morning 30% fat meals, but will explore daily dosing in the evening rather than in the morning.
3. Part 3, will be a 28-day, repeat-dose study in obese subjects. Subjects will receive GSK3008356 (or matching placebo), as 28 daily doses in each of three parallel cohorts. Cohort 1 will evaluate 1 dose strength of GSK3008356 (or matching placebo) administered as morning doses. Cohorts 2 and 3 will evaluate 2 dose strengths (1 per cohort) of GSK3008356 (or matching placebo) administered in the evening.

Please refer to [Figure 1](#) for details.

Figure 1 Study Part Schematic

Part 1 - SD

[figure not shown]
Part 1 – additional cohorts

Part 2 – RD (14d)

Part 3 – RD (28d)

3.1.1. Additional Cohorts for Part 1

Based on emerging PK data, the original planned Part 1 doses were adjusted, per protocol, to 5, 10, 30, 75 and 200 mg (Section 5.3, Figure 1). This was due to a much shorter observed half-life compared to the predicted half-life (1.5-3h observed versus 14.1h predicted).

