4.5. Withdrawal/Stopping Criteria

The following actions must be taken in relation to a subject who fails to attend the clinic for a required study visit:

- The site must attempt to contact the subject and re-schedule the missed visit as soon as possible.
- The site must counsel the subject on the importance of maintaining the assigned visit schedule and ascertain whether or not the subject wishes to and/or should continue in the study.
- In cases where the subject is deemed ‘lost to follow up’, the investigator or designee must make every effort to regain contact with the subject (where possible, 3 telephone calls and if necessary a certified letter to the subject’s last known mailing address or local equivalent methods). These contact attempts should be documented in the subject’s medical record.
- Should the subject continue to be unreachable, only then will he/she be considered to have withdrawn from the study with a primary reason of “Lost to Follow-up”.

A subject may withdraw from study treatment at any time at his/her own request, or may be withdrawn at any time at the discretion of the investigator for safety, behavioural or administrative reasons. If a subject withdraws from the study, he/she may request destruction of any samples taken, and the investigator must document this in the site study records.

[figure not shown]
The reason(s) for not completing the study will be recorded in the case report form (CRF), and the investigator must document, if applicable, the reason (if specified by the subject) for withdrawal of consent. A withdrawn subject may be replaced with another subject who will be assigned to the same treatment randomization.

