6.1.3. Part 2 – Repeat Dose, Morning Dose Administration, Days 2-13

	Days 2-13	
	Pre-dose	0h
Study Drug Dose ⁶		X ⁶
Vital Signs (BP, HR, pulse)	X	
12-Lead ECG ¹	X	
Hematology, Chemistry ²	X	
UA ³	X	
Exploratory PD Labs ³	X	
Plasma PK and Metabolite Sampling ⁴	X	
Adverse Event Review	←=====→	
BSFS ⁵	←=====→	
Concomitant Medication Review	←=====→	

- Day 2 (equal to Day 1 24h time point), 7, 12, and 13 only.
- Day 2 (equal to Day 1 24h time point), 4, and Day 7 only
- Day 2 (equal to Day 1 24h time point) and Day 7 only
- Day 2 (equal to Day 1 24h time point), 4, 5, 6, 12, and 13 only
- The number of BSFS stool types will be collected in real time for each 24h period (Section 11.5).
- For cohorts where multiple doses are to be administered either q1h or q16h, Time 0 is the first dose and subsequent doses are per regimen (q1h or q16) and the subsequent doses are not noted on the T&E Table.

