6.3.5. Electrocardiogram (ECG)

- Triplicate 12-lead ECGs will be obtained for trial eligibility
- Single 12-lead ECGs will be obtained at each timepoint during the study using an ECG machine that automatically calculates the heart rate and measures PR, QRS, QT, and QTcF intervals. Refer to Section 4.5.2 for QTc withdrawal criteria.
- Withdrawal of subjects is to be based on an average QTc value of triplicate ECGs. If an ECG demonstrates a prolonged QT interval, then obtain 2 more ECGs over a brief period of time and then use the averaged QTc values of the 3 ECGs to determine whether the subject should be discontinued from the study
- Continuous cardiac telemetry will be performed. Full disclosures will be reviewed in detail and the review maintained as part of the subject's source documents

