11.2. Appendix 2: Liver Safety Required Actions and Follow up Assessments

Phase I Liver chemistry stopping criteria have been designed to assure subject safety and to evaluate liver event etiology (in alignment with the FDA premarketing clinical liver safety guidance).

<http://www.fda.gov/downloads/Drugs/GuidanceComplianceRegulatoryInformation/Guidances/UCM174090.pdf>.

Phase I liver chemistry stopping criteria and required follow up assessments

Liver Chemistry Stopping Criteria – Liver Stopping Event	
ALT-absolute	
ALT\geq3xULN
 
If ALT\geq3xULN AND bilirubin^{1,2} \geq 2xULN (>35% direct bilirubin) or INR >1.5, Report as an SAE.
 
See additional Actions and Follow Up Assessments listed below

Required Actions and Follow up Assessments following Liver Stopping Event	
Actions	Follow Up Assessments

 • Immediately discontinue study treatment • Report the event to GSK within 24 hours • Complete the liver event CRF, and complete an SAE data collection tool if the event also meets the criteria for an SAE² • Perform liver event follow up assessments • Monitor the subject until liver chemistries resolve, stabilise, or return to within baseline (see MONITORING below) 
MONITORING:
 
If ALT\geq3xULN AND bilirubin \geq 2xULN or INR >1.5
 
 • Repeat liver chemistries (include ALT, AST, alkaline phosphatase, bilirubin) and perform liver event follow up assessments within 24 hrs • Monitor subjects twice weekly until liver chemistries resolve, stabilise or return to within baseline • A specialist or hepatology consultation is 	
 • Viral hepatitis serology³ • Blood sample for pharmacokinetic (PK) analysis, obtained within 7 days of the last dose⁴ • Serum creatine phosphokinase (CPK) and lactate dehydrogenase (LDH). • Fractionate bilirubin, if total bilirubin\geq2xULN • Obtain complete blood count with differential to assess eosinophilia • Record the appearance or worsening of clinical symptoms of liver injury, or hypersensitivity, on the AE report form • Record use of concomitant medications on the concomitant medications report form including acetaminophen, herbal remedies, other over the counter medications. • Record alcohol use on the liver event alcohol intake case report form 
If ALT\geq3xULN AND bilirubin \geq 2xULN or

Liver Chemistry Stopping Criteria – Liver Stopping Event	

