**NOTES :**

- There are also 24-hour assessments of these shown in the protocol. In cases of repeat dose (Part 2), these serve as the pre-dose assessment on the next day. In other cases, they (and 48 and 72 hours) are follow-up assessments on subsequent days, in which case, the target window will be ± 6 hours, but the assessments will be used if they occur on that day.
- \*: Temperature Screening and Day -1 only.

- 
- ECG: Assessment windows are same as those of Vital Signs excluding time points at Checking in (Day -1), 48 hours, and follow-up (Days 6-8) for Part 1
  - Any assessments outside of these time windows will be listed as deviations (not necessarily "important"), but will still be used in the analysis. However, any evaluation which is closer to an adjacent (nominal) time than to its own nominal sampling will not be used

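### The QTc stopping rule removes the subject from the study rather than from treatment, so the remaining planned ECGs lapse and no ECG schedule replaces them

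*Protocol*

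**What the plan says.** Protocol 4.5.2 sets two criteria: QTcF above 500 msec, or a QTc change from baseline above 60 msec. The consequence is that "A subject that meets either bulleted criterion below will be withdrawn from the study". Section 6.3.5 says the same: two further ECGs are taken, and staff "use the averaged QTc values of the 3 ECGs to determine whether the subject should be discontinued from the study". Those two repeats confirm the event. They are the only ECGs that the rule requires.

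Elsewhere the protocol separates leaving treatment from leaving the study. Section 4.5 says "A subject may withdraw from study treatment at any time at his/her own request" and deals with withdrawal from the study in its own sentence. The liver rule in 4.5.1 uses the treatment form: "Study treatment will be discontinued". Appendix 2 (11.2) then sets the follow-up: "Monitor the subject until liver chemistries resolve, stabilise, or return to within baseline". It asks for repeat chemistries within 24h or within 24-72h, then twice-weekly or weekly monitoring, depending on bilirubin and INR.

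The follow-up visit has no 12-lead ECG in Part 1 (Protocol 6.1.1) or in the Part 2 morning schedule (6.1.4). For Part 1, the notes to SAP 11.3.3 confirm that the ECG time points match those for vital signs "excluding time points at Checking in (Day -1), 48 hours, and follow-up (Days 6-8) for Part 1". No Time and Events table has an early-withdrawal column, and SAP 11.7.1 adds no visit for subjects who leave.

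**The concern.** Safety is the primary endpoint in each part, and 12-lead ECGs are among its components (Protocol 2). Section 3.5.1 manages cardiovascular risk through telemetry, ECG and vital-sign monitoring together with this stopping rule. After a QTc signal in a first-in-human study, the next question is whether QTc recovers as the drug clears. The Dose Escalation Committee also reviews flagged ECG findings before it escalates (9.8.1).

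Followed as written, the rule ends the required ECGs in the subjects for whom that question arises. The effect is clearest in the Part 1 single-dose cohorts. The dose has already been given, so the rule cannot reduce exposure. It can only remove assessments.

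**Working it through.** The plan states no figure to reproduce. The check has two parts: a comparison of the two stopping rules, and a count of the planned ECGs that lapse.

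**Comparison of the rules**

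| | QTc rule (4.5.2, 6.3.5) | Liver rule (4.5.1, 11.2) |
|---|---|---|
| Subject leaves | the study | study treatment |
| Measurements to confirm or follow the event at once | two more ECGs before the decision | repeat chemistries within 24h or 24-72h |
| Measurements required afterwards | none stated | weekly or twice weekly |
| End of monitoring | none stated | resolved, stabilised or back within baseline |

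**Part 1, single-dose cohorts 1-6 (Protocol 6.1.1)**

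Post-dose ECGs are at 1, 4, 12, 24 and 72h, which makes 5, with none at follow-up. The number that lapses is 5 minus the number taken up to and including the event:

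- event at 1h: 5 − 1 = 4
- event at 4h: 5 − 2 = 3
- event at 12h: 5 − 3 = 2
- event at 24h: 5 − 4 = 1
- event at 72h: 5 − 5 = 0

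To see what these readings would show, set them against the half-life in Protocol 3.1.1, "1.5-3h observed versus 14.1h predicted". Half-lives elapsed = hours since the event / half-life. After a 1h event:

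- 4h ECG: 4 − 1 = 3h later; 3/3 = 1.0 to 3/1.5 = 2.0 half-lives
- 12h ECG: 12 − 1 = 11h later; 11/3 = 3.7 to 11/1.5 = 7.3 half-lives

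These two planned readings span most of washout. The calculation counts from 1h. If the peak concentration comes later, slightly fewer half-lives have passed at each reading.

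**Part 2, morning schedule (Protocol 6.1.2 to 6.1.4)**

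The footnote to the ECG row for Days 2-13 limits it to "Day 2 (equal to Day 1 24h time point), 7, 12, and 13 only". ECGs after the first dose are therefore:

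- Day 1 at 1, 4 and 12h: 3
- Day 2: 1
- Days 7, 12 and 13: 3
- Day 14 pre-dose, 1, 4 and 12h: 4
- 24h and 72h after the Day 14 dose: 2

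Total: 3 + 1 + 3 + 4 + 2 = 13, with none at follow-up. The SAP's copy of the Day 14 table (11.2.1.5) also marks an ECG at 48h, which makes 14.

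| Event | Taken by then | Lapse, protocol | Lapse, SAP table |
|---|---|---|---|
| Day 1, 1h | 1 | 13 − 1 = 12 | 14 − 1 = 13 |
| Day 7 | 3 + 1 + 1 = 5 | 13 − 5 = 8 | 14 − 5 = 9 |

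After a Day 7 event the next planned ECG is on Day 12, which is 12 − 7 = 5 days later. At 24h per day that is 120h, or 120/3 = 40 to 120/1.5 = 80 half-lives. Keeping the subject in the study would not by itself capture recovery here. Repeat ECGs are needed as well.

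**The case against.** The strongest objection is that a QTc event would be followed anyway. Under 6.3.1.3, SAEs and AEs of special interest as set out in 3.5.1 are followed until they resolve, stabilise or are otherwise explained, and 3.5.1 covers cardiovascular effects and names these stopping criteria. Section 11.3.5 obliges the investigator to carry out supplemental measurements where indicated or requested by the sponsor. An investigator is unlikely to judge a confirmed QTcF above 500 msec clinically unimportant, and resolution cannot be shown without an ECG.

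Most of this stands. A reader might infer that the plan provides no follow-up after a QTc withdrawal, and the documents do not support that. But the duty depends on the event being recorded as an AE or SAE (11.3.1), 3.5.1 never labels any event as being of special interest, and neither section names an ECG or an interval. Sections 6 and 6.3 let safety time points be added during the study in response to new data. That is permission, not a requirement. The inpatient stay and Day 1 telemetry would also let the unit keep watching in practice, but 4.5.2 does not ask for it.

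A second objection concerns reporting. A subject who meets either QTc criterion also crosses a threshold of potential clinical importance in SAP 11.8.2 (above 450 msec, or an increase above 60 msec). Listing 22 (SAP 11.12.5.8) then shows all of that subject's ECGs. This stands too. Unscheduled visits are left out of summary tables and figures (SAP 11.5.3), but it would be wrong to infer that recovery ECGs, once taken, are hidden. With 6 active subjects per cohort, the listing is where one subject's recovery would be read. The gap is whether the ECG has to be taken.

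Third, the protocol has reasons for treating the two risks differently. Dog studies showed hepatic findings, while 3.5.1 rates cardiovascular risk as low on the hERG, rabbit wedge and dog ECG data. That supports a lighter QTc schedule than the liver one. It does not explain ending ECGs that are already planned.

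**Conclusion.** The point holds as a defect in a stated rule. Sections 4.5.2 and 6.3.5 tie a QTc event to leaving the study, which releases the subject from the remaining planned ECGs, and nothing sets a replacement schedule. In the Part 1 single-dose cohorts this affects up to 4 of 5 post-dose ECGs, without reducing exposure. In Part 2 it affects up to 12 of 13 (13 of 14 under the SAP's table).

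These counts assume that the rule is followed literally and that the event falls at a planned ECG. They measure what is no longer required, not what would necessarily go unmeasured, because AE follow-up would probably prompt some ECGs.

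A reader might also infer that this trial lost QTc data. The documents show no such loss. The early stops in SAP 2.2 were for GI reasons or followed discussion between the sponsor and the investigator. The triggering ECG at a planned time and the AE tables are unaffected, and the stopping thresholds are not in question. The correction is worth making because it is cheap and protects follow-up on a component of the primary endpoint.

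**What to change.** Change 4.5.2, and the matching line in 6.3.5, to: *discontinue study treatment; the subject remains in the study for the planned safety assessments, with repeat 12-lead ECGs until QTc returns to baseline or stabilises.* This follows the structure of the protocol's own liver rule.

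Both halves are needed. Staying in the study restores the planned 4h and 12h readings after an early Part 1 event. The repeats cover the five-day gap after a Day 7 event in Part 2.

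The cost is wording in two sections and a few extra ECGs in any affected subject. A general exit visit for everyone who leaves early, with its own SAP status, is not needed to correct this. Listing 22 already shows any ECG obtained.

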4.6. Subject and Study Completion

A completed subject is one who has completed all phases of the study including the follow-up visit.

The end of the study is defined as the last subject's last visit.

5. STUDY TREATMENT

5.1. Investigational Product and Other Study Treatment

The term 'study treatment' is used throughout the protocol to describe any combination of products received by the subject as per the protocol design. Study treatment may therefore refer to the individual study treatments or the combination of those study treatments (Table 6).

Table 6 Study Treatment

	Study Treatment	
Product name:	GSK3008356	Placebo
Formulation description / Dosage form:	Tablet	Tablet
Unit dose strengths/Dosage levels:	0.5, 1, 5, and 25 mg	
Route of Administration	Administered orally	Administered orally
Dosing instructions:	Daily for up to 28 days	Daily for up to 28 days
Physical description:	White Tablet	White Tablet
Manufacturer	GlaxoSmithKline	GlaxoSmithKline

5.2. Treatment Assignment

Subjects will be assigned to treatments in accordance with the randomization schedule generated by Clinical Statistics, prior to the start of the study, using validated software.

A description of each regimen is provided in the table below (Table 7):

Table 7 Regimen Description

Regimen Code	Study Medication	Regimen Code	Study Medication
AA	5 mg GSK3008356, morning dosing	AP	5 mg GSK3008356, evening dosing
BA	10 mg GSK3008356, morning dosing	BP	10 mg GSK3008356, evening dosing
CA	25 mg GSK3008356, morning dosing	CP	25 mg GSK3008356, evening dosing
DA	50 mg GSK3008356, morning dosing	DP	50 mg GSK3008356, evening dosing
EA	75 mg GSK3008356, morning dosing	EP	75 mg GSK3008356, evening dosing
FA	Matched placebo, morning dosing	FP	Matched placebo, evening dosing
GA	125 mg GSK3008356, morning dosing	LA	5 mg GSK3008356 q1h x 9 doses, morning dosing
HA	125 mg GSK3008356 q4h x 2 doses, morning dosing	MA	20 mg GSK3008356 q1h x 9 doses, morning dosing
IA	125 mg GSK3008356 q16h x 2 doses, morning dosing	NA	10 mg GSK3008356 q16h x 2 doses, morning dosing
JA	200 mg GSK3008356, evening dosing	OA	3 mg GSK3008356 q1h x 9 doses, morning dosing
KA	10 mg GSK3008356 q1h x 9 doses, morning dosing	PA	1 mg GSK3008356 q1h x 9 doses, morning dosing

5.3. Planned Dose Adjustments

- This protocol allows some alteration from the currently outlined dosing schedule, but the maximum predicted daily exposure will not exceed $C_{max} = 7.73 \mu\text{g/mL}$ or $AUC 111 \mu\text{g}\cdot\text{h/mL}$.
- The decision to proceed to the next dose level will be made by the GSK Study Team, in conjunction with the investigator based on safety, tolerability and preliminary pharmacokinetic and/or pharmacodynamic data obtained in at least 4 subjects at the prior dose level in Parts 1 and 2 (dose escalation Parts). The actual doses to be administered may be adjusted based on safety, tolerability and preliminary pharmacokinetic and/or pharmacodynamic data at previous dose levels; these dose adjustments may involve either an increase or a decrease in the planned dose.
- The dosing schedule may also be adjusted to expand a dosing cohort to further evaluate safety, pharmacokinetic and/or pharmacodynamic findings at a given dose level, or to add cohorts to evaluate additional dose levels. The study procedures for these additional subject(s) or cohort(s) will be the same as that described for other study subjects. Any cohort expansion or addition will be

contingent on approval of an amended protocol by the Human Research Ethics Committee (HREC).

- If the same Serious Adverse Event occurs in more than one subject, the dose escalation will be temporarily halted and no further subject will be dosed until a full safety review of the data has taken place. Relevant reporting and discussion with the Medical Monitor, relevant GSK personnel, and with the Ethics Committee will then take place prior to any resumption of dosing.
- The above criteria will apply even if measured pharmacokinetic parameters are below the above mentioned PK stopping criteria, and every effort will be made to take a blood sample at the time of the event for pharmacokinetic analysis in the presence of any of the above events.

5.4. Blinding

This will be a double blind (sponsor unblind) study and the following will apply.

- The investigator or treating physician may unblind a subject's treatment assignment **only in the case of an emergency** OR in the event of a serious medical condition when knowledge of the study treatment is essential for the appropriate clinical management or welfare of the subject as judged by the investigator.
- Investigators have direct access to the subject's individual study treatment.
- It is preferred (but not required) that the investigator first contacts the Medical Monitor or appropriate GSK study personnel to discuss options **before** unblinding the subject's treatment assignment.
- If GSK personnel are not contacted before the unblinding, the investigator must notify GSK as soon as possible after unblinding, but without revealing the treatment assignment of the unblinded subject, unless that information is important for the safety of subjects currently in the study.
- The date and reason for the unblinding must be fully documented in the CRF

A subject will be withdrawn if the subject's treatment code is unblinded by the investigator or treating physician. The primary reason for discontinuation (the event or condition which led to the unblinding) will be recorded in the CRF.

- GSK's Global Clinical Safety and Pharmacovigilance (GCSP) staff may unblind the treatment assignment for any subject with an SAE. If the SAE requires that an expedited regulatory report be sent to one or more regulatory agencies, a copy of the report, identifying the subject's treatment assignment, may be sent to investigators in accordance with local regulations and/or GSK policy.

